Appendix D - ACTT-4: Baricitinib/Remdesivir vs Dexamethasone/Remdesivir

ACTT-4, subjects will be contacted by phone, via a telehealth remote visit or in-person visit at approximately 2 months after randomization to assess long term efficacy and safety outcomes.

We anticipate that this trial will require 1348 subjects. Assuming that 8% of subjects are lost to follow-up by Day 29, the total sample size is approximately 1500.

Study Population

Hospitalized adults (≥ 18 years old) with COVID-19 requiring supplemental oxygen administered by low flow, high flow or non-invasive mechanical ventilation modalities.

Inclusion Criteria

1. Hospitalized with symptoms suggestive of COVID-19.
2. Subject (or legally authorized representative) provides informed consent prior to initiation of any study procedures and understands and agrees to comply with planned study procedures.
3. Male or non-pregnant female adults ≥ 18 years of age at time of enrollment.
4. Illness of any duration and has laboratory-confirmed SARS-CoV-2 infection as determined by PCR or other commercial or public health assay (e.g. NAAT, antigen test) in any respiratory specimen or saliva ≤ 14 days prior to randomization.
5. Within the 7 days prior to randomization requiring new use of supplemental oxygen (or increased oxygen requirement if on chronic oxygen) and requires at the time of randomization low or high flow oxygen devices or use of non-invasive mechanical ventilation (ordinal scale category 5 or 6).
6. Women of childbearing potential must agree to either abstinence or use at least one primary form of contraception not including hormonal contraception from the time of screening through Day 29.
7. Agrees not to participate in another blinded clinical trial (both pharmacologic and other types of interventions) for the treatment of COVID-19 through Day 29 (see [Section 5.4](#) for more information about concurrent trial participation).

Exclusion Criteria

1. Prior enrollment in ACTT-3 or ACTT-4. *Note: this includes subjects whose participation in ACTT was terminated early.*
2. On invasive mechanical ventilation at the time of randomization (ordinal scale category 7).
3. Anticipated discharge from the hospital or transfer to another hospital which is not a study site within 72 hours of randomization.
4. Positive test for influenza virus during the current illness (*influenza testing is not required by protocol*).
5. Subjects with a low glomerular filtration rate (eGFR), specifically:
 - a. Subjects with an eGFR 15-30 mL/min are excluded unless in the opinion of the PI, the potential benefit of participation outweighs the potential risk of study participation.
 - b. All subjects with an eGFR < 15 mL/min are excluded.
 - c. All subjects on hemodialysis and/or hemofiltration at the time of screening, irrespective of eGFR, are excluded.

6. Neutropenia (absolute neutrophil count <700 cells/ μ L, $0.7 \times 10^3/\mu$ L).
7. Lymphopenia (absolute lymphocyte count <200 cells/ μ L, $0.20 \times 10^3/\mu$ L).
8. Received five or more doses of remdesivir including the loading dose, outside of the study as treatment for COVID-19.
9. Pregnancy or breast feeding (lactating women who agree to discard breast milk from Day 1 until two weeks after the last study product is given are not excluded).
10. Allergy to any study medication.
11. Received convalescent plasma or intravenous immunoglobulin [IVIg] for COVID-19, the current illness for which they are being enrolled.
12. Received any of the following in the two weeks prior to screening as treatment of COVID-19:
 - More than one dose of baricitinib for the treatment of COVID-19;
 - Other small molecule tyrosine kinase inhibitors (e.g. imatinib, gefitinib, acalabrutinib, etc.);
 - monoclonal antibodies targeting cytokines (e.g., TNF inhibitors, anti-interleukin-1 [IL-1], anti-IL-6 [tocilizumab or sarilumab], etc.);
 - monoclonal antibodies targeting T-cells or B-cells as treatment for COVID-19.

Note: receipt of anti-SARS-CoV-2 mAb prior to enrollment (e.g. bamlanivimab) for their current COVID-19 illness is not exclusionary
13. Use of probenecid that cannot be discontinued at study enrollment.
14. Received 6 mg or more of dexamethasone po or IV (or equivalent for other glucocorticoids) in one day, **on more than one day** in the 7 days prior to time of randomization. *Note: 6 mg dexamethasone dose equivalents include 40 mg prednisone, 32 mg methylprednisolone and 160 mg hydrocortisone.*
15. Received ≥ 20 mg/day of prednisone po or IV (or equivalent for other glucocorticoids) for ≥ 14 consecutive days in the 4 weeks prior to screening.
16. Have diagnosis of current active or latent tuberculosis (TB), if known, treated for less than 4 weeks with appropriate therapy (by history only, no screening required).
17. Serious infection (besides COVID-19), immunosuppressive state, or immunosuppressive medications that in the opinion of the investigator could constitute a risk when taking baricitinib or dexamethasone.
18. Have received any live vaccine (that is, live attenuated) within 4 weeks before screening, or intend to receive a live vaccine (or live attenuated) during the study. *Note: Use of non-live (inactivated) vaccinations including SARS-CoV-2 vaccine is allowed for all subjects.*
19. Had a known VTE (deep vein thrombosis [DVT] or pulmonary embolism [PE]) during the current COVID-19 illness.

Study Intervention

Subjects will be randomized into two arms (1:1).

| Arm 1 | Arm 2 |
|--|--|
| Baricitinib tablets + Placebo IV + Remdesivir IV | Placebo tablets + Dexamethasone IV + Remdesivir IV |

Appendix D - ACTT-4: Baricitinib/Remdesivir vs Dexamethasone/Remdesivir

All subjects will receive standard antiviral treatment with remdesivir as a 200 mg intravenous (IV) loading dose on Day 1, followed by a 100 mg once-daily IV maintenance dose during hospitalization up to a maximum of 10 total doses (i.e., loading + maintenance doses received during study and pre-study if applicable). See [Section 6.1.4](#) for details of dosing and dose modification.

For the baricitinib component, subjects will receive either:

- Baricitinib 4 mg** orally (po) (two 2 mg tablets) or dissolved* per NG tube, daily for the duration of the hospitalization up to a 14-day total course.
- Placebo given as two tablets** orally (po) or dissolved per NG tube, daily for the duration of the hospitalization up to a 14-day total course.

** See MOP for instructions on how to prepare and administer baricitinib to patients having difficulty swallowing*

*** Dose of oral study product will be decreased or held based on eGFR. Specifically:*

| eGFR Value | Dose of Baricitinib/Oral Placebo |
|--|---|
| ≥60 mL/min | Two tablets (4 mg total) once daily No dose adjustment |
| 30 - <60 mL/min | One tablet (2 mg) once daily |
| 15 - <30 mL/min | One tablet (2 mg) QOD – every other day |
| <15 mL/min or require hemodialysis or hemofiltration | Hold oral study product |

For the dexamethasone component, subjects will receive either active product or placebo as follows:

- Dexamethasone will be administered as a 6 mg slow IV push over 3 to 5 minutes (1.5 mL) daily for the duration of the hospitalization up to a 10-day total course.
- A normal saline placebo will be given as a slow IV push over 3 to 5 minutes daily for the duration of the hospitalization up to a 10-day total course
- If local standards use other means of administration (such as IV infusion), these may be used for both active and placebo.
- Any pre-study dexamethasone (max 1 dose per inclusion criteria) is not counted towards the 10 day course.

Duration of therapy:

- IV remdesivir – 5 - 10 days while hospitalized.
 - The recommended treatment duration for most subjects is 5 days.
 - If a patient does not demonstrate clinical improvement, or deteriorates to require invasive mechanical ventilation and/or extracorporeal membrane oxygenation (ECMO), treatment may be extended for up to 5 additional days for a total treatment duration of up to 10 days.
- Oral baricitinib (or oral placebo) – 14 days while hospitalized.
- IV dexamethasone (or IV placebo) – 10 days while hospitalized.
- All medications stop on discharge from hospital.

- Of note, if a subject is retained in the hospital for non-COVID-19 related issues and no longer requires supplemental oxygen and ongoing medical care (i.e., ordinal scale category 3), the PI may decide to discontinue all medications.

1.2 Schedule of Assessments

Table 1. Schedule of Assessments (SOA)

| | Screen | Baseline | Study Intervention Period | Follow-up Visits | | | |
|---|----------------|----------------------|--|-------------------------------|-------------------------------|-------------------------------|----------------------------|
| Day +/- Window | -1 or 1 | 1 | Daily until hospital discharge | 15⁷ ± 2 | 22⁷ ± 3 | 29⁷ + 6 | 60 -7 - +14 |
| ELIGIBILITY | | | | | | | |
| Informed consent | X | | | | | | |
| Demographics & Medical Hx | X | | | | | | |
| Review SARS-CoV-2 results | X | | | | | | |
| Review influenza results if available | X | | | | | | |
| | | | | | | | |
| STUDY INTERVENTION | | | | | | | |
| Randomization | | X | | | | | |
| Administration of investigational agents | | | 
 Remdesivir: IV daily for 5-10 days or until discharge. Baricitinib or placebo: po daily until day 14 or discharge Dexamethasone or placebo: IV daily until day 10 or discharge | | | | |
| | | | | | | | |
| STUDY PROCEDURES | | | | | | | |
| Targeted physical exam ¹ | | X | | | | | |
| Vital sign and NEWS score ¹ | | X | | | | | |
| Clinical data collection ² | | X ⁴ | Daily until discharge ⁸ | X ⁹ | X ⁹ | X ⁹ | X |
| Adverse event evaluation | | | Daily until discharge ⁸ | X ⁹ | X ⁹ | X ⁹ | |
| Concomitant medication review | X | X | From Day -7 to Day 29. Stop collection after discharge | | | | |
| | | | | | | | |
| CLINICAL LABORATORY | | | | | | | |
| Screening clinical lab tests | X ³ | | | | | | |
| Pregnancy test for females of childbearing potential | X ³ | | | | | | |
| Safety hematology, chemistry and liver tests | | X ^{4,5,6,7} | Day 3, 5, 8, 11 (all ± 1 day) if hospitalized ^{6,7} | X ⁹ | | X ⁹ | |
| | | | | | | | |
| RESEARCH LABORATORY FOR ALL SUBJECTS | | | | | | | |
| Blood for plasma to test by PCR for SARS-CoV-2 and cytokines/inflammatory markers | | X ⁴ | Day 3, 5, 8, 11 (all ± 1 day) if hospitalized | | | X ⁹ | |
| Oropharyngeal swab ¹⁰ | | X ⁴ | Day 3, 5, 8, 11 (all ± 1 day) if hospitalized | X ⁹ | | X ⁹ | |

| | | | | | | | |
|---|--|----------------|---|--------------------|--|----------------|--|
| Blood for serum (exploratory and secondary research) | | X ⁴ | Day 3, 5, 8, 11 (all ± 1 day) if hospitalized | X ⁹ | | X ⁹ | |
| ONLY FOR SUBJECTS CONSENTING FOR GENETIC RESEARCH | | | | | | | |
| Blood for RNA for transcriptomic analysis (in PAXgene tube) | | X ⁴ | Day 3, 8 (all ± 1 day) if hospitalized | X ^{9, 11} | | X ⁹ | |

Notes:

¹Targeted physical exam and NEWS (with vital signs) done at baseline. Exam done by the treating licensed healthcare provider may be used. The baseline exam can be one that is conducted from screening to Day 1.

²Refer to [Section 8.1.2](#) of the protocol for details of clinical data to be collected for ordinal score, oxygen requirement, mechanical ventilator requirement, etc.

³Screening clinical laboratory tests include: white blood cell (WBC) count with differential, absolute neutrophil count (ANC), absolute lymphocyte count (ALC), and creatinine. Sites calculate an estimated glomerular filtration rate (eGFR) using the formula selected by the site that is used consistently throughout the study. Laboratory tests performed in the 48 hours prior to enrollment will be accepted for determination of eligibility. A pregnancy test should be done at screening for females of childbearing potential. See [Section 8.1.1](#) for more information about pregnancy tests in post-partum women.

⁴Baseline (Day 1) assessments should be performed prior to first study product administration. Results of Day 1 laboratory assessment do not need to be reviewed to determine if initial study product should be given. In ACTT-4, vitamin D will be assessed on Day 1 only. It will be used to evaluate outcomes and should not be graded as it is not a safety laboratory.

⁵Laboratory tests performed as part of routine clinical care in the 36 hours prior to first dose will be accepted for the baseline (Day 1) safety laboratory tests. Baseline may be the same as the screening laboratory tests.

⁶Safety laboratory tests include: WBC count with differential, hemoglobin, platelet count, creatinine, glucose, total bilirubin, ALT, AST, and INR. D-dimer and C-reactive protein (CRP) are collected at the same time points as the safety labs but should not be graded like the safety labs. D-dimer and CRP may predict severity and support assessment of outcomes.

⁷Any laboratory tests performed as part of routine clinical care within the specified visit window can be used for safety laboratory testing.

⁸Daily until hospital discharge or Day 29, whichever comes first. See [Section 8.1.2.1](#) for more information about doing an ordinal scale assessment on the day after hospital discharge and on the day after a subject dies.

[figure not shown]
⁹In-person visits are preferred but recognizing quarantine and other factors may limit the subject's ability to return to the site for the visit. In this case, the visit may be performed by phone call, home visit or remote telehealth procedure as per institutional standards. If subject is still hospitalized during the follow-up period, they should get Day 15, 22 and 29 assessments along with the daily clinical data collection.

- If still hospitalized at Day 15 and 29 or returns to the site for an in-person visit or home visit: collect clinical data, safety laboratory tests, and research laboratory samples as able.
- If phone call or remote telehealth visit only on Days 15 and 29 and all Day 22 visits: assess adverse events, ordinal scale, readmission to a hospital, and mortality only. At the Day 60 visit, assess oxygen use, physical limitations, readmissions, and clinical outcomes including mortality. See [Section 8.1.2.1](#) for more information.

¹⁰Oropharyngeal swabs are preferred, but if these are not obtainable, nasopharyngeal or nasal swabs may be substituted.

¹¹Subjects who consented for genetic testing and are discharged prior to Day 8 and therefore missing the Day 8 Paxgene tube collection should get blood drawn at Day 15, if feasible.

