6.1.2 Dosing and Administration

Dosing of the medications does not need to occur at the same time. Study Day 1 is the first day any of the 3 study products is administered (i.e., study remdesivir, baricitinib/po placebo, or dexamethasone/IV placebo given on study) and is used to determine timing of protocol assessments and safety analyses as outlined in SOA. Sites have 24 hours between randomization (enrollment) and initial study product administration.

Remdesivir

- Up to four doses of remdesivir are allowed prior to randomization. Remdesivir should be given as soon as possible after randomization. If a patient receives remdesivir in the emergency department late at night or early in the morning on day of enrollment, the dosing may be transitioned to daytime hours if desired by allowing a minimum 12-hour window between the pre-study dose and Day 1 dose.
- After Day 1, remdesivir should be given approximately every 24 hours +/- 2 hours. Protocol deviations do not need to be submitted if remdesivir given outside of this window. Protocol deviations should be submitted if a daily dose is missed completely.
- This dosing should occur as described regardless of the options for anti-inflammatory dosing discussed below.
- All subjects will receive remdesivir as a 200 mg intravenous (IV) loading dose on Day 1, followed by a 100 mg once-daily IV maintenance dose for the duration of the hospitalization up to a 10-day total course. If subjects already received the loading dose prior to study enrollment, then start at 100 mg/day on Day 1. Any doses of remdesivir given prior to enrollment will be counted, so the total duration of remdesivir (i.e. pre-enrollment + on this trial) is 10 days (i.e., a maximum of 10 total infusions). Any doses of remdesivir were administered prior to study enrollment should be documented in Advantage eClinical as a concomitant medication given prior to Day 1. The duration of dosing may be adjusted by the site similar to what is described in the package insert and based on a subject's clinical course and ultimate disease severity.

ANTI-INFLAMMATORY AGENTS (DEXAMETHASONE/IV PLACEBO + BARICITINIB/ PO PLACEBO)

- The anti-inflammatory agents should be given as soon as possible after randomization, but they also should be given around the same time so one arm is not receiving treatment sooner than the other arm.

For patients, who have received dexamethasone before enrollment as part of their clinical care:

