 - Note: If a woman is either postmenopausal (i.e., has had ≥ 12 months of spontaneous amenorrhea) or surgically sterile (i.e., has had a hysterectomy, bilateral ovariectomy (oophorectomy), or bilateral tubal ligation), she is not considered to be of childbearing potential.

- Blood for screening laboratory evaluations, if not done as part of routine clinical care in the preceding 48 hours, should be collected to evaluate the following parameters:

- White blood cell count (WBC) with differential
 - Assess ANC and ALC as per exclusion criteria
- Serum creatinine (and calculate eGFR)
 - Any automated calculation by the clinical laboratory or published formula for this calculation is acceptable. The site should select a formula to be used for all subjects enrolled at the site for the duration of the study.
- Do urine or serum pregnancy test during screening for women of childbearing potential or site may use test done prior to screening during this current hospital admission as long as patient has been confined in hospital since test was done. See instructions below for women who are less than 6 weeks postpartum:
 - Do not do a pregnancy test if the patient is post-partum and has not left the hospital since delivery. The pregnancy test will likely give a false-positive result as serum human chorionic gonadotropin (hCG) is usually detected for up to 4 to 6 weeks after delivery.
 - For women who are less than 6 weeks postpartum and have left the hospital, any positive pregnancy test should be repeated to determine if the HCG is declining as predicted after delivery and therefore the result is a false-positive. Of note, women who are less than 6 weeks postpartum and had heterosexual intercourse since delivery and hospital discharge are unlikely to be pregnant because the average time to first ovulation varies from 45 to 94 days postpartum, with the earliest reported ovulations at 25 and 27 days postpartum.

Clinical screening laboratory evaluations will be performed locally by the site laboratory. The volume of venous blood to be collected is presented in [Table 7](#). A screening lab (i.e., from the hematology and chemistry laboratory panels) may be repeated once if, in the opinion of the investigator, the laboratory abnormality is due to an intercurrent transient condition or it is an aberrant laboratory value.

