The overall eligibility of the subject to participate in the study will be assessed once all screening values are available. The screening process can be suspended prior to complete assessment at any time if exclusions are identified by the study team.

Study subjects who qualify will be randomized in the Advantage eClinical system, and all others will be registered as screen failures. The ordinal scale should be done at the time of randomization; the site will need this data to randomize the subject in eClinical. The study team has 24 hours to complete other Day 1 baseline assessments prior to the first study product administration including the collection of the OP swab and blood and completing or recording a baseline physical examination that was done, including weight and height (height can be self reported). Clinical laboratory tests collected as part of routine care of the patients in the 36 hours prior to first dose qualify for baseline safety tests on Day 1.

If a subject is found to be ineligible AFTER being randomized and they did not receive any study product, the site should file an early study termination and stop all study procedures including specimen collection.

If the subject is found to be ineligible AFTER being randomized and did receive study product, they may continue on study if the PI has no safety concerns with their continued participation. The site should file a study protocol deviation (i.e., checkbox: met exclusion criteria). However, if the PI feels that the risk of participation outweighs the benefit, the site should file an early study termination.

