8.2 Safety and Other Assessments

Study procedures are specified in the SOA. A study physician licensed to make medical diagnoses and listed on the 1572 will be responsible for all trial-related medical decisions.

Physical examination:

A targeted physical examination will be performed at baseline prior to initial study product administration on Day 1. The baseline physical examination can be one that is conducted from screening to Day 1. No routine physical exam is needed for study visits after Day 1. The physical examination DCF will include recording the National Emergency Warning System (NEWS) score and whether or not radiographic infiltrates were identified by imaging studies (chest xray, CT scan).

Study staff at some sites are not allowed into the subject's rooms due to a limited supply of PPE and the need for strict respiratory isolation measures for COVID-19 patients. Because of limited access to subjects, physical exams can be performed by any licensed provider at the study hospital even if they are not study staff listed on the 1572. The study team can extract information from the hospital chart or EMR.

Clinical laboratory evaluations:

- Fasting is not required before collection of laboratory samples.
- Blood will be collected at the time points indicated in the SOA.
 - Clinical safety laboratory tests include WBC, differential, Hgb, PLT, creatinine, glucose, total bilirubin, AST, ALT, and INR.
 - D-dimer, and C-reactive protein are drawn on the same days as the safety laboratory tests but are not safety labs and should not be graded. See SOA.
 - Day 1 clinical laboratory evaluations are drawn prior to initial study product administration as a baseline and results do not need to be reviewed to determine if initial study product administration should be given.
 - On Day 1, Vitamin D levels will be assessed. These will be used to evaluate outcomes and should not be graded.
- Clinical laboratory testing will be performed at each clinical trial site in real time.

Table 7. Venipuncture Volumes for Subjects NOT Consenting for Genetic Testing Involving Transcriptomics Analysis¹

| | Screen | Baseline | | | | | | |
|--|------------------------|------------------------|------------------------|------------------------|------------------------|------------------------|-------------------------------------|-------------------------------------|
| Day +/- Window | -1 to 1 | 1 ± 1 | 3 ± 1 | 5 ± 1 | 8 ± 1 | 11 ± 1 | 15 ± 2 | 29 + 6 |

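### ACTT-4: ALT/AST is a dose-hold parameter with no screening test and no entry limit, and its first required result need not be read before the first dose

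*Protocol*

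**What the plan says.** All references are to Appendix D (ACTT-4) unless stated.

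- **Holds.** Section 6.1.4 holds product on four laboratory parameters: eGFR, ANC, ALC and ALT/AST. Above 10 x ULN, ALT/AST stops both remdesivir and the oral product; each resumes at 5 x ULN or below. The IV dexamethasone/placebo product has no ALT/AST hold.
- **Screening.** Note 3 to the Schedule of Assessments lists a white count with differential, ANC, ALC and creatinine. Section 8.1.1 matches it: "Assess ANC and ALC as per exclusion criteria", plus creatinine for eGFR and a pregnancy test. Neither list contains ALT or AST, and none of the 19 exclusions in 1.1 and 5.2 concerns liver enzymes or liver disease.
- **First liver test.** In Table 1 the row "Safety hematology, chemistry and liver tests" is blank at screening and begins at baseline. Note 5 accepts routine results from the 36 hours before first dose for that panel.
- **Review before dose 1.** Note 4 waives it ("Results of Day 1 laboratory assessment do not need to be reviewed to determine if initial study product should be given"), and section 8.2 repeats the waiver: "results do not need to be reviewed to determine if initial study product administration should be given".
- **Timing.** Section 6.1.2 asks for speed: "Remdesivir should be given as soon as possible after randomization"; and "The anti-inflammatory agents should be given as soon as possible after randomization".

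**The concern.** A hold level is the protocol's own statement of when a product should not be given. For three of the four parameters, screening ensures that nobody starts beyond that level. For ALT/AST nothing does: the first required value comes from a sample that may go unread until after dosing.

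What is at stake is first-dose safety, not inference. Section 2.2.2.1 lists transaminase elevation as a remdesivir risk, and Table 3, footnote b, attributes 4 of the 11 remdesivir discontinuations for adverse reactions in ACTT-1 to raised transaminases (3 + 1). Section 2.2.3.1 lists liver-enzyme changes among the baricitinib label precautions.

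**Working it through.** No sample size, power or error rate is involved, so the check sets the sections side by side.

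**Step 1. Hold parameters against screening and entry limits**

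| Parameter | Hold level (6.1.4) | Product held | Screening test (note 3, 8.1.1) | Entry limit (1.1, 5.2) |
|---|---|---|---|---|
| eGFR | < 15 mL/min | remdesivir, oral | yes | < 15 excluded; 15-30 only if the PI judges benefit to outweigh risk |
| ANC | < 500 cells/µL | oral | yes | < 700 excluded |
| ALC | < 200 cells/µL | oral | yes | < 200 excluded |
| ALT/AST | > 10 x ULN | remdesivir, oral | no | none |

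Three of four have a screening test and an entry limit at or stricter than the hold level. ALT/AST has neither.

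**Step 2. Does anything else force a result to be read before dose 1?**

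- The Day 1 panel contains ALT and AST (note 6), but its review is waived twice (note 4, 8.2).
- Section 6.1.4 says standard-care results should also be used if available. That helps when a result exists; it does not require one.
- Note 5 lets a recent routine result serve as baseline. It does not require that result to be read before dosing.
- Section 7.1.1 lets the investigator stop product for severe laboratory abnormalities, which presupposes a known value.
- Tables 7 and 8 show a combined screening-and-safety row that mentions liver tests, with 10 mL at screening. These are blood-volume tables; the two test lists and Table 1 do not place ALT/AST at screening.

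None closes the gap for a patient whose routine result is absent or whose Day 1 result is pending or unread.

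**Step 3. Exposure per affected patient**

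Once the Day 1 result is read, the remdesivir rule applies, because it is triggered by a value being found. Exposure is then normally one remdesivir infusion (200 mg, or 100 mg if the loading dose was given before the study) and one oral dose, which is active in Arm 1 only. The oral rule is worded for a value that arises on study, so it does not plainly cover one already present at baseline.

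**Step 4. Comparison with ACTT-3**

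Appendix C has the same kind of Day 1 waiver, but its section 8.1.1 screens ALT/AST and its section 5.2 excludes values above 5 x ULN. The waiver leaves no such gap there.

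**The case against.** The strongest reply is that the protocol already covers most patients. They are inpatients with a new or increased oxygen requirement; many will have routine liver tests, and 6.1.4 directs sites to use them. Testing is prompt: "Clinical laboratory testing will be performed at each clinical trial site in real time". Harm requires no available or read result together with a true value above 10 x ULN. This stands as a limit on size, but no rule requires a result to be read before dose 1.

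A second reply is that the hold targets on-treatment change, and that dropping the ACTT-3 limit may have been deliberate: remdesivir was by then approved, and up to four doses may precede randomization, so the first study dose need not be the first exposure. The protocol gives no reason either way. A reader might infer an internal contradiction or an oversight; the text supports neither. A hold need not also be an entry limit, and this is a safety improvement rather than a correction of conflicting statements.

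A third reply is reassurance on harm: Appendix C, section 2.2.2.1, reports no hepatotoxicity difference between remdesivir and placebo in preliminary ACTT-1 data. That stands as a reason to expect limited harm. The ACTT-2 experience with baricitinib is weaker support, since section 2.1.1 says that trial had exclusions for liver dysfunction.

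A fourth reply concerns the remedy. Holding the oral product on Day 1 after randomization would leave an Arm 1 patient with no active anti-inflammatory while Arm 2 proceeds with dexamethasone, although 6.1.2 wants both agents given close together so that neither arm starts earlier. Open-label cover under 6.1.4 is offered only after more than 2 days and, with blinded tablets, could add steroid to Arm 2 patients already on dexamethasone. This is correct, and it is why the check belongs before randomization.

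**Conclusion.** The point holds as a narrow, inexpensive safety improvement. ALT/AST is the only laboratory hold parameter in ACTT-4 that is neither screened nor limited at entry, and the plan as written permits a first dose of remdesivir and oral product above 10 x ULN when no routine result is available or read.

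The number affected cannot be computed, because no baseline ALT/AST distribution or rate of routine testing is given; it is probably small. There is no effect on power or the primary comparison.

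A reader might infer up to three daily doses: the next scheduled liver test is Day 3 ± 1, that is Day 2, 3 or 4, with 1, 2 or 3 doses before it. That assumes the site overlooks a Day 1 result already in hand. Section 6.1.4 expects scheduled safety laboratories to guide dosing, so with the plan followed the exposure is normally one dose.

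**What to change.** 1. Amend notes 3 and 4 and sections 8.1.1 and 8.2 so that one ALT/AST result is reviewed before randomization. It may be a routine result from the 48-hour screening window or from the 36 hours before first dose, or else the baseline sample. The waiver can stay for the other Day 1 tests.
2. State in 1.1 and 5.2 that a patient is not randomized while ALT or AST is above 10 x ULN. This follows the pattern for eGFR, ANC and ALC, where the entry limit is at or stricter than the hold. Section 5.5 already allows one rescreen after an abnormal laboratory finding.
3. Secondary: reword the oral-product rule in 6.1.4 so that it also covers a value present at baseline.

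**Cost.** Wording edits, and no test beyond those already planned: ALT/AST is drawn before first dose and run locally, note 5 lets screening and baseline share a sample, and Tables 7 and 8 already budget blood at screening. Where the baseline sample is the source, it must be drawn and read before randomization rather than in the window now allowed ("The study team has 24 hours to complete other Day 1 baseline assessments prior to the first study product administration"). The downside is a short wait for patients with no recent routine liver test, and a few patients deferred or not enrolled.
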